2.3.3 Training protocols

All participants allocated to each training group will exercise 3 days/week at the same time of the day, with 24 h of interval between sessions. Those enrolled in resistance training will perform 3 sets of 2 bilateral leg exercises (leg press and seated calf raise). In the first week, the load intensity will be set at 15-18 maximal repetitions. From then on, the load intensity will be performed over 8-12 maximal repetitions.

The supramaximal training regimen will consist of 30 s of supramaximal cycling exercise (MonarkErgomedic 894E®), interspersed with 4 min of active recovery, using a relative load equivalent to 7.5% of the individual body mass. During the first four weeks of training, participants will complete two 30s all-out sprints per session. From then on, volume will be increased to four 30s all-out sprints per session.

Endurance training will be performed on a motorized treadmill (Jaeger®,

Laufergotest, Germany). During the first week of training, relative intensity will be set at 65–75% $\text{VO}_{2\text{max}}$ and each training session will last 30–40 min. From then on, the duration of the training sessions will be increased to 40–50 min and the treadmill speed will be set to elicit 75–85% $\text{VO}_{2\text{max}}$

2.3.4 Exercise Performance

2.3.4.1 Resistance training group

Both before as well as after training, participants will be evaluated for maximal and submaximal knee extension strength. Measurements will be taken in the seated position, with the participants maintaining their knee flexed at 70° (69). MVC will be determined based on the highest peak torque obtained in 3 trials, interspersed by 60 s of passive recovery. Then, participants will be asked to maintain 40% of MVC until failure. Visual feedback from the dynamometer software will be provided. Task termination will occur whenever the participants exhibit strength decrements $\geq 10\%$ for more than 10 s.

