The most common methods to examine the effects of group III and IV afferents is to maintain ischemia after a fatiguing contraction or trough intramuscular injection of a hypertonic saline solution (58). Recently, Norbury et al. (2021) (59) observed that induced muscle pain by hypertonic saline solution injection reduces endurance exercise performance through the exacerbation of neuromuscular fatigue, which origins in inhibitory feedback from group III/IV nociceptors, reducing central motor output. Muscle afferents adjust the motoneuronal responses induced by the stimulation at the cervicomedullary level (corticospinal pathway) during exhaustive contraction. Such motoneuronal activation might be affected rather by changes in the corticospinal excitability, altering the effectiveness of the motor unit recruitment as indicated by the amplitude of cervicomedullary motor evoked potentials (CMEPs) or thoracic motor evoked potentials (TMEPs) measured through transcranial magnetic stimulation (TMS) (60). For the upper-limbs, Martin et al., (2006) (61) verify that after 2-min MVC of the homonymous or antagonists muscles the decrease of the CMEPs on elbow extensors was maintained post contraction by holding the muscle ischemic with a cuff inflated, and this was attributed to the maintained discharge of group III and IV afferents. Despite this, the same effect was not observed for the elbow flexors muscles (62, 61). For the lower-limbs, surprisingly, Kennedy et al., (2016) (63) showed that maintaining fire of group III and IV afferents with ischemia post 2 min MVC of the homonymous or antagonists' muscles had no effect on knee extensors TMEPs. Unlike CMPEs or TMEPs pathway, H-reflex, apart from motoneuronal excitability, is also influenced and allows to assess pre and pos synaptic inhibition mechanisms (60). It was observed that H-reflex amplitude diminishes during sustained submaximal contractions at 25% and 50% MVC of the abductor pollicis brevis muscle (64). Also, H-reflex amplitude evoked in the wrist flexor muscles is reduced by metabosensitive group III and IV afferents activation, trough hypertonic saline solution injection, suggesting that the spinal motor reflex activity seems to be uniformly affected by inputs from these afferents (65). Not only the evidence is somewhat conflicting regarding the TMS research, it is important to note that in the H-reflex above-mentioned studies (64, 65), the effects of induced muscle fatigue

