isometric contraction followed by blood-flow occlusion) Vs. a control condition (no isometric contraction nor blood flow occlusion), on H-reflex recruitment curve and V wave excitability (aim #1). Since the activation of group III/IV afferents can inhibit the corticospinal pathway (61) we hypothesize that the normalized maximal amplitude and the slope of the ascending limb of the H-recruitment curve will decrease with metaboreflex activation. Additionally, we intend to examine the acute impact of different exercise modalities (resistance, supramaximal and endurance) on nociception sensibility (by the application of a cold tolerance test and by determining pressure pain threshold) (aim #2). This will allow us to investigate the role of different acute exercise paradigms on possible metaboreflex desensitization in its relationship with altered neuromuscular responses at post-exercise time point (attenuated inhibition of H-reflex and V-wave amplitude during metaboreflex activation). Also, once past research has shown that muscle metaboreflex activation reduces the sensitivity of the baroreflex (68), we will measure arterial pressure (AP) and heart rate variability (HRV) during cold pain tolerance testing. Despite all exercise modalities could enhance reducing pain sensibility after exercise, we hypothesize that resistance and supramaximal exercise stimuli will enhance nociceptive tolerance via metaboreflex desensitization compared to that seen with endurance exercise (attenuated increase of AP and sympathetic component of HRV during cold pressor test). Finally, we intend to explore the impact of long-term resistance, supramaximal and endurance training on nociceptive sensibility, using the same tests of aim #2 (aim #3). We hypothesize that chronic EIH will be of greater magnitude after supramaximal and resistance exercise training vs. endurance training. In addition, we hypothesize that decreased nociception will be related with attenuated inhibition of H-reflex and V-wave amplitude and attenuated increase of AP and sympathetic component of HRV during metaboreflex activation after training and this will result in increased exercise performance via heightened H-reflex and V-wave excitability.

2. Research Plan and Methods

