2.4.2 MVC (aim #1, #2 and #3)

All neuromuscular assessments will be made on the participants' dominant lower limb (plantar-flexors), using a Biodex System 3 Pro isokinetic dynamometer (Biodex Medical System 3). All testing sessions will be conducted between 07:00 and 11:00 hours, to avoid daily variations in muscle strength related to human circadian rhythms. Measurements will be taken in the seated position, with the participants maintaining their hips and knee flexed at 120° and ankle at 110° of plantar flexion (70). The flexed position at the knee joint will be used to reduce the mechanical contribution of the gastrocnemii to the plantar-flexor torque. Participants will be asked not to alter their posture and to focus on the task. MVC and rate of torque development (RTD) will be determined for plantar flexor muscles, based on three isometric contractions, lasting 5 s each. A 60 s interval of rest will be respected between trials. Participants will be instructed to exert their maximum force as fast and hard as possible with verbal encouragement and visual feedback from the dynamometer software being provided. The highest peak torque value will be defined as the participants MVC value (72, 73).

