2.4.3 Surface EMG (aim #1, #2 and #3)

Surface EMG will be recorded continuously from EMG electrodes placed on soleus and anterior tibial muscles (Delsys DE 2.x series EMG sensors). After skin preparation, a 2-slot adhesive interface will be applied on the EMG sensor to firmly stick the sensor to the skin. A conductive reference electrode will be placed around the left ankle of each participant (36). Surface EMG signals will be band-pass filtered (10 – 2000 Hz) and amplified using a Delsys Bagnoli-8 amplifier to a total gain of 1000. Then, a 16-bit analog-to-digital converter (National Instruments, USB-6251) will be used to sample the signal at 10 kHz. EMG data will be recorded in synchrony with the torque signal originating from the Biodex System, using [name] software (Knud

Larsen, SMI, Aalborg University) (73).

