2.4.4 Percutaneous Electrical Nerve Stimulation (aim #1, #2 and #3)

A constant-current isolated stimulator (STIMSOLA, Biopac Systems; Inc; CA, US) will be used to stimulate posterior tibial nerve. The cathode electrode (8 mm diameter, Ag-AgCl) will be placed on the popliteal fossa and the anode (5 x 10 Compex, Medical SA) proximal to the patella. Each participant will receive a range of electrical stimuli (1-40 mA) to determine the position eliciting the greatest response with the minimum stimulus intensity. The optimal position will be identified using a handheld cathode ball electrode. Finally, stimulation electrode will be fixed with rigid straps and taping (72, 73).

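### Aim #3, resistance group: the exploratory reflex-to-performance correlation pairs a plantar-flexor reflex with a knee-extensor outcome, although a same-muscle strength measure is already collected

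*Combined protocol and SAP*

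**What the plan says.** Section 1.3 sets out the aim #3 hypothesis as a chain. Training lowers nociception, this goes with less inhibition of the H-reflex and V-wave, and "this will result in increased exercise performance via heightened H-reflex and V-wave excitability". Section 2.4.13 then plans to explore correlations that involve pain, performance, H-reflex, V-wave, arterial pressure and heart rate variability.

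For the resistance group, section 2.3.4.1 states that "participants will be evaluated for maximal and submaximal knee extension strength". The two measures are a seated knee-extension MVC and the time that 40% of it can be held. No other performance outcome is given for this group.

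The reflex side sits in another muscle group. Section 2.4.2 places all neuromuscular assessments on the "dominant lower limb (plantar-flexors), using a Biodex System 3 Pro isokinetic dynamometer". Section 2.4.3 has "EMG electrodes placed on soleus and anterior tibial muscles". Under section 2.4.4 a constant-current stimulator "will be used to stimulate posterior tibial nerve". Sections 2.4.5 to 2.4.7 use this arrangement for the H-recruitment curves, the V-waves and the metaboreflex trials, in which the conditioning contraction is plantar flexion. No quadriceps EMG and no femoral nerve stimulation is described.

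**The concern.** The hypothesis says that performance rises by way of the reflex change. A direct test would measure both in the same muscle. As planned, this group's test asks whether a soleus reflex change goes with a change in knee-extensor torque or hold time, and the plan gives no reason to expect that it should.

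Both possible results are then ambiguous. A null correlation could mean that the mechanism is absent, or that it operates in the plantar flexors and was looked for in the wrong muscle. A positive correlation could reflect the mechanism, or only that men who respond well to training improve in both muscle groups. At stake is the mechanistic part of aim #3 in one of three groups. The running and cycling tests of the other two groups are whole-body tasks that include the plantar flexors, so the complete separation of muscles arises only here.

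**Working it through.** The plan states no figure for this link, so the main check is to set the sections side by side.

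| Element (aim #3, resistance group) | Muscle or nerve | Section |
|---|---|---|
| Performance: MVC and 40% MVC hold | Knee extensors | 2.3.4.1 |
| MVC and rate of torque development (RTD) | Plantar flexors | 2.4.2 |
| EMG | Soleus, anterior tibial | 2.4.3 |
| Stimulation | Posterior tibial nerve | 2.4.4 |
| H-recruitment curve, 10% MVC background | Plantar flexors | 2.4.5 |
| V-wave during MVC | Tibial nerve | 2.4.6 |
| Metaboreflex contraction, 25% MVC | Plantar flexors | 2.4.7 |
| Training | Leg press and seated calf raise | 2.3.3 |
| Local pressure pain site | Rectus femoris | 2.4.8 |

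Three things follow.

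1. No reflex is recorded in the muscle group in which performance is measured.
2. A same-muscle strength measure exists. Section 2.4.2 covers aim #3 and yields plantar-flexor MVC and RTD, section 2.4.12 describes how RTD is derived, and seated calf raise trains that muscle group.
3. The plan does not connect that measure to the hypothesis. Section 2.3.2 lists neuromuscular adaptations separately from performance, and section 2.4.13 does not name plantar-flexor strength in its correlation sentence.

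**How much a within-group correlation can show.** Section 2.3.1 recruits 30 men for three groups, so 30/3 = 10 per group, or 10 × (1 − 0.20) = 8 after the stated attrition of about 20%. The three groups' performance outcomes differ in kind (torque and hold time, distance, number of sprints), so raw values cannot be pooled directly and n is about 8 to 10. I assume a two-sided 5% level; section 2.4.13 gives p < 0.05 without sidedness.

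- Smallest significant correlation: r = t/√(n − 2 + t²). For n = 8, t = 2.447 and r = 2.447/√(6 + 5.99) = 0.707. For n = 10, t = 2.306 and r = 2.306/√(8 + 5.32) = 0.632.
- True correlation needed for 80% power (Fisher z): r = tanh[(1.960 + 0.842)/√(n − 3)]. For n = 8 this is tanh(2.802/2.236) = 0.849. For n = 10 it is tanh(2.802/2.646) = 0.785.
- Power for assumed true correlations: 1 − Φ(1.960 − atanh(r)·√(n − 3)).

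| Assumed true r | Power, n = 8 | Power, n = 10 |
|---|---|---|
| 0.3 | 10% | 13% |
| 0.5 | 23% | 31% |
| 0.7 | 49% | 63% |

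The correlation has little room for weakening by a change of muscle. Equally, pairing the right muscles will not give it good power. The gain is in what the estimate means.

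**The case against.** Knee extension is a defensible performance test for this group. Leg press is trained, and section 2.4.8 takes the local pressure pain threshold on the rectus femoris. The hypothesis starts from reduced nociception, so a knee-extensor outcome lines up with the local pain measure. This stands, and it is why the test should stay.

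A reader might infer that the hold should move to plantar flexion. The documents do not support that as a simple gain. It would align performance with the reflex but separate it from the local pain site. Section 2.3.2 also puts performance on the same day as the neuromuscular tests, and the visible text does not give their order, so a plantar-flexor hold to failure could fatigue the muscle being recorded.

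A reader might also take section 1.2 as evidence that these afferents do not act in the knee extensors, since ischaemia after a maximal contraction "had no effect on knee extensors TMEPs". That result concerns motor evoked potentials, not the H-reflex. The same section calls it surprising, describes the stimulation evidence as conflicting, treats the H-reflex separately, and suggests that spinal reflex activity is affected by these afferents in a uniform way. It cannot be used to argue that the mechanism is absent there.

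Finally, the analysis is exploratory and plantar-flexor strength is already analysed before and after training as a neuromuscular adaptation. Both are true, and they keep the point small. They do not remove it, because the one analysis that addresses the hypothesised link does not name that measure.

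**Conclusion.** The mismatch is real and follows from the text alone: for the resistance group, the plan as written tests a plantar-flexor mechanism against a knee-extensor outcome. It affects one exploratory correlation in one group of about 8 to 10 men. It does not touch the comparisons of pain, arterial pressure, heart rate variability or reflex outcomes.

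Its size cannot be given as a number. A reader might multiply an assumed same-muscle correlation by an assumed correlation of gains between muscles to obtain a loss of explained variance. The documents give neither value, and the result would only restate the assumptions. It would also require the link to run solely through the plantar flexors, whereas section 1.2 treats the V-wave as sensitive to supraspinal input and section 1.3 names reduced nociception as the driver.

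Nor is this the only group in which a muscle-specific check is possible: section 2.4.2 applies to all aim #3 participants. What is particular to the resistance group is that its performance test leaves the recorded muscle out as a target altogether. The conclusion is a modest one: a better-matched analysis is available from data already planned, and the plan should use it.

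**What to change.** Leave section 2.3.4.1 as it is, with knee extension as the resistance-group performance outcome. Add to section 2.4.13, in substance:

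*For the resistance training group, the correlation of performance with changes in H-reflex and V-wave variables will use the pre-to-post change in plantar-flexor MVC and voluntary RTD measured under section 2.4.2. The corresponding correlations with knee-extension MVC and hold time will be reported as a secondary, cross-muscle analysis. Both are exploratory.*

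Section 2.4.12 derives RTD in three time windows, so naming one window in advance would keep the added set small. Results are best given as estimates with confidence intervals, in view of the group size.

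The cost is wording only; no test, visit or participant burden is added. The downsides are one further set of exploratory correlations at low power, and that plantar-flexor strength has a same-muscle measure while plantar-flexor endurance does not, so the hold keeps only its cross-muscle reading.

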2.3.4.2 Endurance training group

Exercise performance will be determined based on the maximal distance completed by each participant in response to a time-trial run. For the time-trial run, both before and after training, participants will be asked to endure a submaximal treadmill running for as long as possible at the speed compatible with 50% of the distance between the 1st ventilatory threshold and $\text{VO}_{2\text{max}}$ ($\Delta 50$ speed).

Before each time trial, on a different day, participants will complete a treadmill ramp protocol to volitional exhaustion. This test will be used with two specific purposes: 1) to determine participants $\text{VO}_{2\text{max}}$, 1st ventilatory threshold, and the $\Delta 50$

speed; 2) to prescribe the treadmill running speeds for the training period.

2.3.4.3 Supramaximal training group

Both before as well as after training, participants will perform the maximal number of 30 s maximal all-out cycling trials (70), interspersed by a 4-minute of active recovery period, until mean power value decreases to 50% of the first supramaximal bout.

2.4 Common methodology

2.4.1 Participants (aim #1, #2 and #3)

Recreationally active men aged 18-30 years will be recruited. Women will not be included once responses to experimental pain have been demonstrated to vary according to the menstrual cycle phase (71). Participants will be recruited from the local communities and from the Faculty surroundings via word-of-mouth for this study. Exclusion criteria will include known metabolic, cardiovascular, respiratory, orthopedic disease and taking medication for the treatment of pain or having any pain related conditions. Each participant will complete a health- screening as well as a physical activity questionnaire and baseline measures (body mass, height and blood pressure). Finally, participants will be provided with verbal information about the requirements and demands of the study and required to give written, informed consent to the experimental procedures, which was approved by the Faculty of Human Kinetics ethics committee (CEFMH N°33/2021) and according with the Declaration of Helsinki. Participants will be told to avoid strenuous physical activity 24 hr, caffeine ingestion 4 hr and analgesics intake 6 hr prior to each testing session (59).

2.4.2 MVC (aim #1, #2 and #3)

All neuromuscular assessments will be made on the participants' dominant lower limb (plantar-flexors), using a Biodex System 3 Pro isokinetic dynamometer (Biodex Medical System 3). All testing sessions will be conducted between 07:00 and 11:00 hours, to avoid daily variations in muscle strength related to human circadian rhythms. Measurements will be taken in the seated position, with the participants maintaining their hips and knee flexed at 120° and ankle at 110° of plantar flexion (70). The flexed position at the knee joint will be used to reduce the mechanical contribution of the gastrocnemii to the plantar-flexor torque. Participants will be asked not to alter their posture and to focus on the task. MVC and rate of torque development (RTD) will be determined for plantar flexor muscles, based on three isometric contractions, lasting 5 s each. A 60 s interval of rest will be respected between trials. Participants will be instructed to exert their maximum force as fast and hard as possible with verbal encouragement and visual feedback from the dynamometer software being provided. The highest peak torque value will be defined as the participants MVC value (72, 73).

2.4.3 Surface EMG (aim #1, #2 and #3)

Surface EMG will be recorded continuously from EMG electrodes placed on soleus and anterior tibial muscles (Delsys DE 2.x series EMG sensors). After skin preparation, a 2-slot adhesive interface will be applied on the EMG sensor to firmly stick the sensor to the skin. A conductive reference electrode will be placed around the left ankle of each participant (36). Surface EMG signals will be band-pass filtered (10 – 2000 Hz) and amplified using a Delsys Bagnoli-8 amplifier to a total gain of 1000. Then, a 16-bit analog-to-digital converter (National Instruments, USB-6251) will be used to sample the signal at 10 kHz. EMG data will be recorded in synchrony with the torque signal originating from the Biodex System, using [name] software (Knud

Larsen, SMI, Aalborg University) (73).

2.4.4 Percutaneous Electrical Nerve Stimulation (aim #1, #2 and #3)

A constant-current isolated stimulator (STIMSOLA, Biopac Systems; Inc; CA, US) will be used to stimulate posterior tibial nerve. The cathode electrode (8 mm diameter, Ag-AgCl) will be placed on the popliteal fossa and the anode (5 x 10 Compex, Medical SA) proximal to the patella. Each participant will receive a range of electrical stimuli (1-40 mA) to determine the position eliciting the greatest response with the minimum stimulus intensity. The optimal position will be identified using a handheld cathode ball electrode. Finally, stimulation electrode will be fixed with rigid straps and taping (72, 73).

2.4.5 Standard H-recruitment curves (aim#3)

Before and after long-term training, standard methods will be used for M-wave and H-reflex recordings (52). These measurements will be taken while each participant maintains a submaximal low intensity contraction of the plantar flexors (10% MVC) with visual feedback from the dynamometer software being provided. The upper current intensity will be determined, firstly, by progressively increasing the current intensity by 5 mA from 0 until there is no further increase in peak torque or in peak-to-peak M-wave amplitudes. At each intensity level, three stimuli will be delivered at 3-seconds intervals. To construct the H-recruitment curves, the upper current intensity (compatible with maximal M-wave) will be divided into 22 segments equally separated on a logarithmic scale, with 16 stimuli/intensity randomly applied to construct the recruitment curves, delivered at 3s intervals.

